3.5 Safety Assessment

Safety Population will be the primary population for the safety analyses. All safety endpoints will be summarized descriptively by treatment group and overall. No statistical inference will be applied to the safety endpoints.

3.5.1 *Adverse Events (AEs)*

AEs will be categorized by primary system organ class and preferred term as coded using the current MedDRA version category designation.

An overview of treatment-emergent AEs (TEAEs) will be provided including counts and percentages of participants with the following:

- Any TEAEs (overall and by maximum severity)
- Any TEAEs (non-serious)
- Any study drug related TEAEs (overall and by maximum severity)
- Any TEAEs leading to discontinuation of study drug
- Any treatment-emergent serious AEs (TESAEs)
- Any study drug related TESAEs
- Any TEAEs leading to death.

The TEAEs described above will be summarized separately by system organ class and preferred term. The non-serious TEAEs occurring in more than 2% of participants in any treatment group and preferred term will be summarized.

Listings will be presented specifically for TEAEs, TESAEs and TEAEs leading to discontinuation of study drug and TEAEs leading to death.

3.5.2 *Event of Special Interest*

Events of special interest (ESIs) include the following: hepatic abnormalities, muscle-related abnormalities, new-onset diabetes mellitus (NODM) and/or hyperglycemia, renal abnormalities, changes to antihypertensive medication(s) due to changes in blood pressure, and macular degeneration described as follows:

- AST or ALT > 3×ULN;
- Total bilirubin > 2×ULN;
- Creatine kinase (CK) > 5 × ULN;
- NODM or worsening of glycemic control;

Note: NODM is defined by 1 or more of the following criteria, based upon information from AE, medication, and laboratory data:

- AE indicating new type 1 or type 2 diabetes;

- Initiation of anti-diabetes medication with confirmation of the diagnosis of diabetes by blinded external review by experts in diabetology;
- HbA1c $\geq 6.5\%$ (≥ 0.065 hemoglobin fraction); and/or
- Two consecutive values of fasting plasma glucose that are ≥ 126 mg/dL (≥ 7.0 mmol/L).

Note: Worsening of glycemic control will be defined as HbA1c increase from Baseline $>0.5\%$ (>0.005 hemoglobin fraction) and/or a new concomitant medication or increase in current antidiabetic therapy in a participant with a Baseline HbA1c $\geq 6.5\%$ (≥ 0.065 hemoglobin fraction)

- A $>25\%$ decrease in eGFR from Baseline or an eGFR < 30 mL/min/1.73 m², calculated using the Chronic Kidney Disease Epidemiology Collaboration equation, and/or an increase in serum creatinine of ≥ 0.3 mg/dL (≥ 26.5 μ mol/L) from Baseline;
- Changes to antihypertensive medication(s) due to changes in blood pressure in those participants receiving antihypertensive medication(s) treatment at Baseline and those participants not receiving antihypertensive medication(s) treatment at Baseline; and
- Macular degeneration.

An overview of ESIs described above will be provided including counts, percentages of participants by treatment group, and a listing of each ESI.

Values and changes from baseline will be summarized for ALT, AST, and total bilirubin by visit and treatment group. The number and percent of participants with abnormal values for ALT, AST, and total bilirubin will be summarized. These summaries of participants with abnormal values will be performed overall; by normal Baseline; and by abnormal Baseline for ALT, AST, and total bilirubin individually. Hy's Law criteria ($>3 \times \text{ULN}$ for either ALT or AST, with accompanying total bilirubin $>2 \times \text{ULN}$) will also be applied to the data. Any potential Hy's Law cases will be listed separately.

Values and changes from Baseline will be summarized for CK levels by visit and treatment group and visit. In addition, the number and percent of participants with abnormal CK values will be summarized. These summaries of participants with abnormal CK values will be performed overall, by normal Baseline CK, and by abnormal Baseline CK. Values of CK from Baseline to EOT will be summarized by treatment group and by Baseline eGFR category.

Cases of NODM will be recorded and summarized using the appropriate system organ class. These events will be summarized by severity and relationship to study drug for each treatment group. Fasting plasma glucose and HbA1c will be monitored as specified in [Table 1 Schedule of Procedures](#).

Baseline eGFR will be summarized by treatment group for actual value and for Baseline eGFR categories. Shift tables of eGFR category from Baseline to EOT will be provided by treatment group. Shift tables of urine albumin-creatinine ratio and urine protein-creatinine ratio from Baseline to EOT will be provided by treatment group.

Participants will be identified as those who had a diagnosis of hypertension in their medical history and received antihypertensive medication(s) at Baseline. If participants had an adverse event related to hypertension after Baseline (see [Appendix B](#) for preferred terms) and had any change in antihypertension medication within 30 days of the start date of the adverse event, that change

in antihypertension medication will be considered as due to a change in blood pressure. The number and percentage of participants will be summarized by treatment group.

Participants will be identified who did not have a prior diagnosis of hypertension in their medical history and did not receive antihypertensive medication(s) at Baseline. If participants had an adverse event of hypertension and initiated antihypertension medication within 30 days of the start date of the adverse event, the adverse event will be classified as a change in blood pressure. The number and percentage of participants will be summarized by treatment group.

Cases of macular degeneration will be recorded and summarized using the appropriate system organ class. These events will be summarized by severity and relationship to study drug for each treatment group.

3.5.3 *Clinical Laboratory Tests*

Blood and urine samples for clinical laboratory evaluations (including a full serum chemistry panel, hematology, coagulation, and urine dipstick analysis) will be collected at visits specified in [Table 1](#). A limited serum chemistry panel will also be collected as specified in Table 1. All safety laboratory samples should be collected while the participant is fasting (a minimum of 8 hours) and prior to the next dose of study drug (at applicable visits). Urinalysis will be performed locally by dipstick analysis from a sample of mid-stream urine. See clinical protocol ([Appendix B](#)) for a complete list of analytes.

Laboratory values will be summarized descriptively, including the change from Baseline. In addition, shift tables for all parameters will be presented to describe the change in laboratory parameter values at end of treatment visit using normal range categories (low, normal, and high).

Chemistry and hematology laboratory parameters will be listed.

3.5.4 *Vital Signs*

Vital signs (heart rate and blood pressure) measured in triplicate prior to study administration at applicable visits as indicated in Table 1. Values will be summarized with descriptive statistics, including the change from Baseline at each visit by treatment group and overall.

Additional summaries of blood pressure measurements will be performed, within treatment group and time point, using counts of triplicate means that meet the following criteria:

- Systolic blood pressure:
 - ≥ 160 mmHg
 - ≥ 180 mmHg
 - change from Baseline by ≥ 20 mmHg
- Diastolic blood pressure:
 - ≥ 100 mmHg
 - ≥ 110 mmHg
 - change from Baseline by ≥ 15 mmHg.

As described above, the number and percentage of participants receiving antihypertensive medications at Baseline with changes to antihypertensive medications due to change in blood pressure will be summarized by treatment group. The number of participants who were not hypertensive or on any antihypertensive medications at Baseline, but started one or more antihypertensive drugs during the treatment period, will be summarized by treatment group.

Vital signs will be listed.

3.5.5 *Electrocardiograms*

A single 12-lead ECG will be performed at Visit 2 and Visit 7/EOT/ET and will be read locally.

ECG parameters will be recorded as normal, abnormal or not done. Abnormal values will be assessed as clinically significant or not clinically significant. Counts and percentages for ECG parameters will be summarized by treatment group and in total.

3.5.6 *Physical Examinations*

Physical examinations (with focused examination on general, respiratory, CV, abdominal, and extremities evaluations) and recording of weight and height will be performed at Screening Visit and Visit 7/EOT/ET. Height will be measured at Screening Visit only and used to calculate body mass index. BMI will be calculated as weight/(height/100)² (kg/m²); rounded and displayed to 1 decimal place.

Physical examination, parameters, will be recorded as normal, abnormal or not done. Abnormal values will be assessed as clinically significant or not clinically significant. Count and percentages for physical parameters will be summarized by treatment group and in total.

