4.2 Exclusion Criteria

Participants who meet any of the following criteria will be excluded from participation in the study:

1. Have current or any previous history of New York Heart Association class III or IV heart failure (HF) or left ventricular ejection fraction <30%;
2. Have been hospitalized for HF within 5 years prior to Screening;
3. Have had any of the following clinical events within 3 months prior to Screening:
 - Non-fatal MI;
 - Non-fatal stroke;
 - Non-elective coronary revascularization; and/or
 - Hospitalization for unstable angina and/or chest pain.
4. Have uncontrolled severe hypertension, defined as either systolic blood pressure ≥ 160 mmHg or diastolic blood pressure ≥ 100 mmHg prior to Randomization taken as the average of triplicate measurements. One triplicate retest will be allowed during the same visit, at which point if the retest result is no longer exclusionary, the participant may be randomized;
5. Have a formal diagnosis of homozygous FH;
6. Have active liver disease, defined as any known current infectious, neoplastic, or metabolic pathology of the liver; unexplained elevations in alanine aminotransferase (ALT) or aspartate aminotransferase (AST) $>3 \times$ upper limit of normal (ULN); or total bilirubin $>2 \times$ ULN at Screening;

Note: An abnormal ALT, AST, or total bilirubin must be confirmed by a repeat abnormal measurement at least 1 week apart.

7. Have glycosylated hemoglobin (HbA1c) $\geq 10.0\%$ (≥ 0.100 hemoglobin fraction) or a fasting glucose ≥ 270 mg/dL (≥ 15.0 mmol/L) at Screening;
8. Have thyroid-stimulating hormone $>1.5 \times$ ULN at Screening;
9. Have creatine kinase (CK) $>3 \times$ ULN at Screening;
10. Have a history of a malignancy that required surgery (excluding local and wide local excision), radiation therapy, and/or systemic therapy during the 3 years prior to Randomization;
11. Have a known history of alcohol and/or drug abuse within 5 years prior to Randomization;
12. Have received treatment with other investigational products or devices within 30 days of Screening or 5 half-lives of the previous investigational product, whichever is longer;

Note: Participants who have received treatment for COVID-19 with standard of care and/or emergency use authorization medications, including vaccinations and boosters, within 30 days of Screening or 5 half-lives of the previous investigational product **will** be permitted.

13. Are taking gemfibrozil;

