8.1.4 Events of Special Interest

ESIs will be monitored over time by the independent DSMB, as described in the DSMB charter, regardless of whether these events were reported as AEs. Any events that qualify as an AE or SAE will be reported accordingly (see [Sections 8.1, 8.2, and 8.3](#)).

ESIs will include the following hepatic abnormalities, muscle-related abnormalities, new-onset diabetes mellitus (NODM) and/or hyperglycemia, renal abnormalities, changes to antihypertensive medication(s) due to changes in blood pressure, and ophthalmic events (ie, macular degeneration), described as follows:

- AST or ALT $>3 \times$ ULN;
- Bilirubin $>2 \times$ ULN;
- CK $>5 \times$ ULN;
- NODM or worsening of glycemic control;

Note: NODM is defined by 1 or more of the following criteria, based upon information from AE, medication, and laboratory data:

- AE indicating new type 1 or type 2 diabetes;
- Initiation of anti-diabetes medication with confirmation of the diagnosis of diabetes by blinded external review by experts in diabetology;
- HbA1c $\geq 6.5\%$ (≥ 0.065 hemoglobin fraction); and/or
- Two consecutive values of fasting plasma glucose that are ≥ 126 mg/dL (≥ 7.0 mmol/L).

Note: Worsening of glycemic control will be defined as an HbA1c increase from Baseline $>0.5\%$ (>0.005 hemoglobin fraction) and/or a new concomitant medication or increase in current antidiabetic therapy in a participant with a Baseline HbA1c $\geq 6.5\%$ (≥ 0.065 hemoglobin fraction).

- A >25% decrease in eGFR from Baseline or an eGFR <30 mL/min/1.73 m², calculated using the Chronic Kidney Disease Epidemiology Collaboration equation, and/or an increase in serum creatinine of ≥ 0.3 mg/dL (≥ 26.5 μ mol/L) from Baseline;
- Changes to antihypertensive medication(s) due to changes in blood pressure in those participants receiving antihypertensive medication(s) treatment at Baseline; and
- Macular degeneration.

These ESIs will be monitored through review of the AE and laboratory database.

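### The laboratory criteria for new-onset diabetes carry no Baseline-diabetes or post-Baseline condition, so under the literal rule a known, stable diabetic counts as new-onset

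*SAP*

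**What the plan says.** SAP 3.5.2 lists new-onset diabetes mellitus (NODM) or worsening of glycemic control among the events of special interest (ESIs). It says "NODM is defined by 1 or more of the following criteria, based upon information from AE, medication, and laboratory data". Protocol 8.1.4 opens its definition identically: "NODM is defined by 1 or more of the following criteria". The four criteria in both documents are:

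1. "AE indicating new type 1 or type 2 diabetes";
2. start of anti-diabetes medication, with the diagnosis confirmed by blinded external review;
3. HbA1c of 6.5% or more;
4. "Two consecutive values of fasting plasma glucose that are" at or above 126 mg/dL.

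Worsening of glycemic control is defined next to it, as a rise in HbA1c from Baseline of more than 0.5% and/or "a new concomitant medication or increase in current antidiabetic therapy in a participant with a Baseline HbA1c" of 6.5% or more.

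Protocol 4.2, criterion 7, excludes only HbA1c of 10.0% or more or fasting glucose of 270 mg/dL or more. SAP 3.3.4 and 3.4.4 plan diabetes (yes or no) and HbA1c above 6.4% as Baseline categories and subgroups. Under SAP 3.5.2 the ESIs are reported as counts and percentages by arm, with a listing. Under Protocol 8.1.4 the DSMB monitors ESIs from the AE and laboratory database, whether or not they were reported as AEs.

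**The concern.** An incidence measure needs a population at risk. The definition does not name one, and its two laboratory criteria do not ask whether the value is new. Since participants with established diabetes can enrol, people who already had the condition can be counted as having developed it on study.

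The outputs at stake are the ESI overview, the ESI listing and the DSMB's ESI monitoring. There the NODM percentage would mix prevalent and incident diabetes, would be too high in both arms, and would show a weaker relative contrast than the incident cases alone.

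The SAP takes Baseline status into account for other safety variables. In 3.5.2 it separates participants with treated hypertension at Baseline from those with neither diagnosis nor treatment, and it summarises ALT, AST, bilirubin and CK by normal and abnormal Baseline. NODM has no such step, although its meaning depends on Baseline status more directly.

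**Working it through.** The documents give no diabetes prevalence and no expected NODM rate, so there is no figure of theirs to reproduce. The check is one of text, followed by an illustration.

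**Step 1. Is the rule restricted anywhere?**

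- SAP 3.5.2 and Protocol 8.1.4: the AE criterion contains the word new, and the medication criterion requires initiation plus confirmation of the diagnosis. The HbA1c and glucose criteria have no condition on history, Baseline value or timing.
- Protocol 8.1.4.3 speaks of diabetes newly diagnosed on study, but refers back to 8.1.4 for how.
- Protocol 9.2.2.1 and the reporting text in SAP 3.5.2 name no at-risk group or denominator for NODM.
- SAP 3.3.4 and 3.4.4 use Baseline diabetes for description and subgroups, and do not link it to NODM.
- The worsening definition mentions Baseline HbA1c of 6.5% or more, but does not remove those participants from NODM.

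HbA1c and fasting glucose are in both the full and the limited chemistry panel (Protocol Appendix B), so qualifying values can recur. Take a participant with known diabetes and HbA1c of 7.5% at Baseline and throughout. The glycaemic exclusion does not apply (7.5% is below 10.0%), criterion 3 is met (7.5% is at least 6.5%), and HbA1c has not changed. Under the rule as written this is NODM.

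**Step 2. How many could be miscounted?**

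Inputs: N = 300, randomized 2:1, so about 200 and 100 (Protocol 3.1). Assumed: diabetes at Baseline p = 10–20%; share of those with HbA1c of 6.5% or more q = 50–75%.

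Miscounted = N × p × q

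- Low: 300 × 0.10 × 0.50 = 15 (10 obicetrapib, 5 placebo)
- High: 300 × 0.20 × 0.75 = 45 (30 obicetrapib, 15 placebo)

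**Step 3. What happens to the contrast?**

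Let t be the true NODM rate among participants without diabetes at Baseline. The reported rate per arm is pq + (1 − p)t. Take t = 4% on obicetrapib and 2% on placebo, purely for illustration: ratio 2.0, difference 2.0 points.

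| p | q | Obicetrapib | Placebo | Ratio | Difference (points) |
|---|---|---|---|---|---|
| 10% | 50% | 5.0 + 3.6 = 8.6% | 5.0 + 1.8 = 6.8% | 1.26 | 1.8 |
| 10% | 75% | 7.5 + 3.6 = 11.1% | 7.5 + 1.8 = 9.3% | 1.19 | 1.8 |
| 20% | 50% | 10.0 + 3.2 = 13.2% | 10.0 + 1.6 = 11.6% | 1.14 | 1.6 |
| 20% | 75% | 15.0 + 3.2 = 18.2% | 15.0 + 1.6 = 16.6% | 1.10 | 1.6 |

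Over a wider range (p = 5–20%, q = 50–80%) the ratio runs from 1.43 to 1.09. The term pq cancels in the difference, which is (1 − p) × 2.0 points, or 1.9 to 1.6 over that range. These are expected values with the same p and q in both arms.

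**The case against.** The strongest reply is that the term explains itself. The event is called new-onset, the AE criterion says new, Protocol 8.1.4.3 speaks of new diagnosis, and Protocol 8.1 treats conditions present at Screening as medical history unless they change. A separate worsening category suggests a split between new and existing disease. SAP section 7 also defers detail to separate programming specifications, which may contain the restriction. This stands as evidence of intent: a reader might infer that the sponsor chose to count known diabetics, and the documents do not support that. But intent is not a derivation. The text does not say whether Baseline diabetes comes from history, medication, HbA1c or glucose, or which denominator applies, so two programmers could produce different counts.

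A reader might also infer that the rule would hide a glycaemic signal. That goes too far. Safety is descriptive and no risk ratio is planned (SAP 3.5). The NODM summary by severity and relationship to study drug looks AE-based, so it would be less affected. SAP 3.5.3 provides change from Baseline and end-of-treatment shift tables for laboratory values, and every ESI is listed and can be checked against Baseline. The expected absolute difference also barely moves.

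Finally, a reader might infer that the worsening category shuts out diabetics with Baseline HbA1c below 6.5%. The sentence is ambiguous, and the qualifier may govern only the medication limb. Nor does a small drift demonstrate such a gap: 6.3% to 6.6% is a rise of 0.3 points and misses the limit of more than 0.5% whatever the Baseline value.

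**Conclusion.** The point holds as a defect in the stated derivation. Under the literal rule, known and stable diabetics count as new-onset in the ESI overview, the ESI listing and the DSMB's ESI monitoring. On the assumed prevalence (10–20%) and share above threshold (50–75%), about 15 to 45 of 300 participants would be miscounted, and an illustrative true ratio of 2.0 would appear as about 1.10 to 1.26. Neither assumption comes from the documents, so the size is indicative only.

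The consequence is an inflated percentage and a diluted relative contrast. No hypothesis test is affected. The DSMB charter and the programming specifications were not available, so a restriction may exist there; the protocol and SAP contain none.

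**What to change.** Before unblinding, in both SAP 3.5.2 and the ESI definition in Protocol 8.1.4:

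- Define diabetes at Baseline from data already collected: medical history, antidiabetic medication, and Baseline HbA1c or glucose at the documents' own thresholds.
- Derive NODM from post-Baseline data only, in participants without diabetes at Baseline, with that group as the denominator in each arm.
- Report worsening of glycemic control separately among participants with diabetes at Baseline.
- State whether the qualifier of Baseline HbA1c of 6.5% or more applies to both limbs of the worsening definition or only to the medication limb.

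The cost is a small wording change in two documents and one added derivation, with no new data collection. Changing the SAP alone would leave it at odds with the protocol definition of the ESIs that the DSMB monitors.

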9.2.2.1 Analysis of ESIs

Liver-associated enzymes and total bilirubin will be summarized by the value and change from Baseline in the value, by treatment group and visit. In addition, the number and percent of participants with abnormal values for ALT, AST, and total bilirubin will be summarized. These

summaries of participants with abnormal values will be performed overall; by normal Baseline; and by abnormal Baseline for ALT, AST, and total bilirubin individually. Hy's Law criteria ($>3 \times \text{ULN}$ for either ALT or AST, with accompanying total bilirubin $>2 \times \text{ULN}$) will also be applied to the data. Any potential Hy's Law cases will be listed separately.

CK levels will be summarized by the value and change from Baseline in value, by treatment group and visit. In addition, the number and percent of participants with abnormal CK values will be summarized. These summaries of participants with abnormal CK values will be performed overall, by normal Baseline CK, and by abnormal Baseline CK. Values of CK from Baseline to EOT will be summarized by treatment group and by Baseline eGFR category.

Cases of NODM will be recorded and summarized using the appropriate system organ class. These events will be summarized by severity and relationship to study drug for each treatment group. Fasting plasma glucose and HbA1c will be monitored as specified in [Appendix A](#).

Baseline eGFR will be summarized by treatment group for actual value and for Baseline eGFR categories. Shift tables of eGFR category from Baseline to EOT will be provided by treatment group. Shift tables of urine albumin-creatinine ratio and urine protein-creatinine ratio from Baseline to EOT will be provided by treatment group. Muscle-related abnormalities will be summarized by treatment group and by Baseline eGFR category.

The number and percentage of participants receiving antihypertensive medication(s) treatment at Baseline with changes to antihypertensive medication(s) due to changes in blood pressure will be summarized by treatment group.

Cases of macular degeneration will be recorded and summarized using the appropriate system organ class. These events will be summarized by severity and relationship to study drug for each treatment group.

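### SAP 3.5.2 adds a hypertension-history condition to the antihypertensive-change ESI, leaving two groups, one of them inside the protocol definition, with no attribution rule

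*SAP*

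**What the plan says.** Protocol 8.1.4 lists the ESI as "Changes to antihypertensive medication(s) due to changes in blood pressure in those participants receiving antihypertensive medication(s) treatment at Baseline". Protocol 8.1.4.5 describes follow-up for the same population. Protocol 9.2.2.1 plans the matching summary: "The number and percentage of participants receiving antihypertensive medication(s) treatment at Baseline with changes to antihypertensive medication(s) due to changes in blood pressure". None of the three mentions a history of hypertension.

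The ESI list in SAP 3.5.2 widens the population to "those participants receiving antihypertensive medication(s) treatment at Baseline and those participants not receiving antihypertensive medication(s) treatment at Baseline", again without a history condition. It then promises an output on that basis: "An overview of ESIs described above will be provided including counts, percentages of participants by treatment group, and a listing of each ESI".

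Later in SAP 3.5.2 comes the rule that decides when a medication change is attributed to blood pressure. For the first group: "Participants will be identified as those who had a diagnosis of hypertension in their medical history and received antihypertensive medication(s) at Baseline". A change counts if it falls within 30 days of the start of a hypertension-related adverse event, with terms taken from Appendix B. The second group are those who "did not have a prior diagnosis of hypertension in their medical history and did not receive antihypertensive medication(s) at Baseline". For them the trigger is an adverse event of hypertension followed by a new antihypertensive within 30 days, and Appendix B is not cited.

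SAP 3.5.4 returns to the topic under vital signs. One sentence begins "As described above, the number and percentage of participants receiving antihypertensive medications at Baseline with changes to antihypertensive medications". The next counts participants "who were not hypertensive or on any antihypertensive medications at Baseline, but started one or more antihypertensive drugs during the treatment period".

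SAP section 6 lists four changes from the protocol.

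**The concern.** An operational rule should cover the population it serves. Here the definition is by medication, in the protocol and in the SAP list, while the rule is by medication and history together. A participant on an antihypertensive at Baseline with no hypertension entry in the medical history meets the protocol definition, yet the SAP has no means of classifying a later change as blood-pressure related. The same holds for a participant with a recorded diagnosis and no Baseline medication, whom the SAP list includes.

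At stake is a named safety count. All safety endpoints in this trial are descriptive, so the count by arm is itself the result, and both documents name blood pressure and ESIs as items the DSMB will monitor. A count that departs from the protocol definition without saying so is hard to interpret.

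**Working it through.** The plan states no figure for this item, so there is nothing to reproduce. The check crosses hypertension history with Baseline antihypertensive medication and reads each text against the four cells.

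| History | Baseline medication | Protocol 8.1.4, 8.1.4.5, 9.2.2.1 | SAP 3.5.2 list | SAP 3.5.2 attribution rule |
|---|---|---|---|---|
| Yes | Yes | in | in | yes |
| No | Yes | in | in | none |
| Yes | No | out | in | none |
| No | No | out | in | yes |

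1. Protocol definition: 2 cells are in and 1 of them has a rule (1 of 2).
2. SAP list: 4 cells are in and 2 of them have a rule (2 of 4).
3. Could the uncovered cells be empty by design? Nothing in the documents makes them so. Exclusion criterion 4 (Protocol 4.2) removes only uncontrolled severe hypertension, at or above 160 mmHg systolic or 100 mmHg diastolic. An antihypertensive can be taken for another indication, and a recorded diagnosis can be untreated at Baseline.
4. Does SAP 3.5.4 fill the gap? Its sentence on medicated participants names no history condition but opens by referring back. It may import the whole 3.5.2 rule, history filter included, or only the adverse-event-plus-30-days attribution. It supplies no rule of its own. Its sentence on new starters covers only the no-history, no-medication cell, needs no adverse event or 30-day link, and is not tied to a change in blood pressure. Neither sentence covers diagnosed but unmedicated participants.
5. Is the departure declared? The four changes in SAP section 6 are removal of the word fasting, subgroup analyses, extra trough levels and unequal variances. None of the 4 concerns this ESI.
6. Do the two rules use the same terms? Appendix B has 23 terms: 17 for raised or uncontrolled pressure, 6 non-directional and 0 for a fall (17 + 6 + 0 = 23). Only the rule for the medicated group cites it.
7. Direction of the effect: relative to the protocol, the rule loses the medicated, no-history cell and gains the unmedicated, no-history cell. The documents give no cell sizes or event rates, so neither the size nor the sign of the net effect on the ESI total can be derived.

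**The case against.** The best defence is that the history condition is a deliberate indication filter. It keeps out people who take these drugs for reasons other than hypertension, and the no-history, unmedicated group isolates new-onset cases. The new-onset part stands: grouping unmedicated participants by medication alone would mix untreated known hypertension with new onset, so the split should be kept there. For the medicated group the documents give no such reason, and the filter removes participants whom the protocol counts.

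A reader might infer that SAP 3.5.2 and 3.5.4 contradict each other outright, that the SAP holds three different rules for unmedicated participants, or that several tables must show different numbers under one name. The text does not support this. The first sentence of 3.5.4 can be read as adopting the 3.5.2 rule in full. The new-starter count is a separate summary, and Protocol 8.8.1 leaves vital-sign abnormalities to be defined in the SAP. The ESI list is a definition, not an attribution rule. The section is ambiguous, which is less than a conflict.

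A reader might also infer that blood-pressure events in the two groups vanish from the report. They do not. Adverse-event tables and listings (SAP 3.5.1), blood-pressure threshold counts (3.5.4) and the concomitant-medication listing (3.3.6) remain, and the DSMB sees unblinded blood pressure.

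Whether falls in blood pressure should count is largely settled: both rules require a hypertension event, and Appendix B has no term for a fall.

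Finally, SAP section 7 defers detail to separate programming specifications, which are not available here. They might address the gap, but the population for a protocol-defined ESI belongs in the SAP.

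**Conclusion.** The point holds in a limited form. The firm mismatch is between the attribution rule in SAP 3.5.2 on one side and the protocol and the SAP's own ESI list on the other. Applied literally, the rule omits from the ESI count the events of one group inside the protocol definition and of a second group inside the SAP list only. Section 6 records neither the narrowing nor the added unmedicated group.

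This rests on reading the rule as the sole attribution rule; no other appears in either document. It assumes nothing about how many participants are in the uncovered groups. The effect is confined to a descriptive safety summary; the primary endpoint, type I error and power are untouched. Confidence is high in the wording mismatch, while its practical consequence is unknown. Low priority, but worth correcting before unblinding because the repair is cheap.

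**What to change.** Changes to the SAP:

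- (a) In 3.5.2, remove the hypertension-history condition from the medicated group so that it matches the protocol. Keep the attribution by adverse event plus medication change within 30 days.
- (b) In 3.5.2, extend the unmedicated rule to participants with a diagnosis but no Baseline medication. Show them separately from those with no hypertension history, so that the new-onset count is kept.
- (c) Apply the Appendix B terms to both groups.
- (d) In 3.5.4, state that the medicated count uses the 3.5.2 rule and that the new-starter count is a separate vital-signs summary.
- (e) In section 6, list the added unmedicated group as a change from the protocol.

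The cost is a few sentences and a small programming change. No new data are needed, because medical history, adverse events and medication start and stop dates are already collected. The downside of (a) is that participants taking an antihypertensive for another indication enter the medicated denominator; the hypertension adverse-event condition still limits the numerator.
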